### **12.4 Genetic Testing**

At Visit 1/Screening, for those subjects who do not have confirmation of their clinical diagnosis of X-linked or lamellar ichthyosis, blood or buccal samples will be collected for genetic testing. As/if required, this test may be repeated during the study as determined by the investigator (e.g., specimen quality, loss or handling concerns, indeterminate outcome). The subject may be enrolled based upon their clinical diagnosis only, with genetic testing to follow, such that the results are available at or before the conclusion of the study. Specifics regarding the testing options for these two ichthyosis subtypes, specimen handling, and related matters will be determined by the company used for genetic testing. In the event the genetic testing results do not concur with the clinical diagnosis the subject may complete the study as the inclusion criteria are based upon the clinical assessment of their skin disease by the Investigator at Baseline.

### **13. END OF STUDY CRITERIA**

At the end of each subject's participation in the study, the investigator will complete an End of Study form for all completed and discontinued subjects.

#### **13.1 Completion of the Study**

Subjects who complete the 12 week course of treatment as specified in this protocol and all of the Visit 9/Day 84 evaluations will have completed the study.

#### **13.2 Subject Discontinuation**

A subject may be withdrawn from the study prior to completion for any of the following reasons:

- AE
- Death
- Lack of efficacy
- Lost to follow-up
- Noncompliance with study drug
- Physician decision
- Pregnancy
- Progressive disease
- Protocol deviation
- Study terminated by Sponsor
- Withdrawal by subject; Note: if the subject decides to withdraw from the study due to an AE then it should be classified as withdrawal due to an AE.
- Other (e.g., any other reason that may affect the outcome of the study or the safety of subjects)

If a subject withdraws from the study prematurely for any reason, the site should make every effort to have the subject return for the next scheduled visit to complete the final visit procedures. When a subject is withdrawn from the study for a test article related AE (i.e., possibly, probably or definitely related as defined in [Section 14](#)), when possible, the subject should be followed until resolution or stabilization of the AE. If the subject is discontinued from the study due to pregnancy, the pregnancy and its outcome should be followed.

Subjects who are prematurely withdrawn or discontinued from the study will not be replaced.

#### **13.3 Study Termination**

The study may be terminated by the investigator or the Sponsor. If, in the opinion of the investigator, clinical observations made during the study suggest that it may be unwise to continue, he or she may stop the study. A study termination by the investigator will be reported to the Sponsor.

In addition, a written statement fully documenting the reasons for this action will be submitted to the Sponsor by the investigator within five working days.

In the event that the Sponsor chooses to discontinue or terminate the study, appropriate notification will be given to the investigator.

#### **14. ADVERSE EVENT REPORTING**

An **adverse event** is any untoward medical occurrence associated with the use of a drug in humans, whether or not considered drug related.

An AE (also referred to as an adverse experience) can be any unfavorable and unintended sign (e.g., an abnormal laboratory finding), symptom, or disease temporally associated with the use of a drug, without any judgment about causality. An AE can arise from any use of the drug (e.g., off-label use, use in combination with any drug) and from any route of administration, formulation or dose, including an overdose.

Information on the medical condition of subjects should begin following the subject's written informed consent/assent to participate in the study and a medical history should be taken at screening. During any wash out and baseline periods, any changes in the health of subjects should be recorded as changes in medical history unless an event occurred as a result of a study-related procedure and is unanticipated; in such cases, the event should be recorded as an AE and reported to the Institutional Review Board (IRB) as an "unanticipated problem" in accordance with local procedures. Other changes in subject health information becomes AE data when the subject begins dosing with the test article; therefore AE data should be collected from the date of the first dose of test article until the date of the final study visit. These data are considered TEAEs.

Timely and complete reporting of all AEs assists the Sponsor or designee in identifying any untoward medical occurrence, thereby allowing:

- 1) protection of the safety of study subjects;
- 2) a greater understanding of the overall safety profile of the test article;
- 3) recognition of dose-related test article toxicity;
- 4) appropriate modification of study protocols;
- 5) improvements in study design or procedures; and
- 6) adherence to worldwide regulatory requirements.

Test article is defined as a pharmaceutical form of an active ingredient (or "primary operational component" for devices) or vehicle/placebo being tested or used as a reference in the study, whether blinded or unblinded. AEs may be either spontaneously reported or elicited during questioning and examination of a subject. All AEs must be completely recorded on the AE CRF. If known, the investigator should report the diagnosis of the underlying illness or disorder, rather than its individual symptoms. Subjects experiencing AEs that cause interruption or discontinuation of test article, or those experiencing AEs

that are present at the end of their participation in the study should receive follow-up as appropriate. If possible, report the outcome of any AE that caused permanent discontinuation or that was present at the end of the study particularly if the AE is considered by the investigator to be treatment-related (i.e., definitely, probably, or possibly related to test article).

#### 14.1 Adverse Event

All AEs must be recorded on the AE CRF. AEs should be followed to resolution or stabilization (if possible), and reported as serious adverse events (SAEs) if they become serious.

No human studies have been conducted with PAT-001 (isotretinoin) Ointment. The most common adverse reactions associated with other topical retinoid formulations include application site erythema, skin exfoliation, pain of skin, application site pruritus, skin irritation, skin tenderness, skin burning sensation, application site stinging, dry skin/lips, skin hyperpigmentation, skin hypopigmentation, and photosensitivity. The most notable or common adverse reactions with oral isotretinoin are: dry lips, dry skin, back pain, dry eye, arthralgia, epistaxis, headache, nasopharyngitis, chapped lips, dermatitis, renal or hepatotoxicity, musculoskeletal discomfort, teratogenicity, and visual acuity reduced. Although systemic exposure is expected to be low given the route of topical administration and therefore many of these risks are unlikely, these, as well as other unknown risks, are considered potential risks pending clinical experience with this new dosage form.

The investigator will instruct the subject to report any AEs that may occur during the study. At each visit, the investigator should ask the subject, in non-directive fashion, about any change in the subject's overall condition since the previous visit.

The severity of each AE, as judged by the investigator, will be recorded on the appropriate AE CRF and will be graded according to the following scale:

**Mild** – The AE is transient and easily tolerated by the subject.

**Moderate** – The AE causes the subject discomfort and interrupts the subject's usual activities.

**Severe** – The AE causes considerable interference with the subject's usual activities, and may be incapacitating or life-threatening.

The investigator must determine the relationship of the AE to the test article according to the following categories:

**Definite** – An event that follows a reasonable temporal sequence from administration of the test article; that follows a known or expected response pattern to the test article; and that is confirmed by improvement on stopping or reducing

the dosage, and reappearance of the event on repeated exposure (re-challenge).

**Probable** – An event that follows a reasonable temporal sequence from administration of the test article; that follows a known or expected response pattern to the test article; and that is confirmed by improvement on stopping or reducing the dosage of the test article; and that is unlikely to have been caused by concurrent/underlying illness or other drugs, procedures, or other causes.

**Possible** – An event that follows a reasonable temporal sequence from administration of the test article; that follows a known or expected response pattern to the test article; but may have been caused by concurrent/underlying illness, other drug, procedure, or other causes.

**Unlikely** – An event that does not follow a reasonable temporal sequence from administration of the test article; that does not follow a known or expected response pattern to the test article, or most likely was caused by concurrent/underlying illness, other drug, procedure, or other causes, because of their known effects.

**Not Related** – An event almost certainly caused by concurrent/underlying illness, other drug, procedure, or other causes.

The investigator should categorize the outcome of the AE according to the following categories:

**Fatal** – Termination of life as a result of an AE.

**Not Recovered/Not Resolved** – AE has not improved or the subject has not recuperated.

**Recovered/Resolved** – AE has improved or the subject has recuperated.

**Recovered/Resolved with Sequelae** – subject recuperated but retained the pathological conditions resulting from the prior disease or injury.

**Recovering/Resolving** – AE is improving or the subject is recuperating.

**Unknown** – Not known, not observed, not recorded or subject refused.

An **adverse reaction** is any AE caused by a drug. Adverse reactions are a subset of all suspected adverse reactions for which there is reason to conclude that the drug caused the event. For the purposes of prescription drug labeling, the term adverse reaction means an undesirable effect, reasonably associated with the use of a drug that may occur as part of its pharmacological action or may be unpredictable in its occurrence.

A **suspected adverse reaction** is any AE for which there is a reasonable possibility that

the drug caused the event.

For the purposes of IND safety reporting, “reasonable possibility” means there is evidence to suggest a causal relationship between the drug and the AE. A suspected adverse reaction implies a lesser degree of certainty about causality than adverse reaction, which means any AE caused by a drug.

An AE or suspected adverse reaction is considered “unexpected” if it is not listed in the investigator brochure (IB) or is not listed at the specificity or severity that has been observed; or, if an IB is not required or available, is not consistent with the risk information described in the general investigational plan or elsewhere in the current application. For example, under this definition, hepatic necrosis would be unexpected (by virtue of greater severity) if the IB referred only to elevated hepatic enzymes or hepatitis. Similarly, cerebral thromboembolism and cerebral vasculitis would be unexpected (by virtue of greater specificity) if the IB listed only cerebral vascular accidents. “Unexpected,” as used in this definition, also refers to AEs or suspected adverse reactions that are mentioned in the IB as occurring with a class of drugs or as anticipated from the pharmacological properties of the drug, but are not specifically mentioned as occurring with the particular drug under investigation.

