### 10.4 Local Skin Reactions

At each clinic visit (except Visit 1/Screening), LSRs including burning/stinging, pain, and pruritus will be documented in each Treatment Area using a four-point ordinal scale where 0=none, 1=mild, 2=moderate, and 3=severe. These LSRs will be collected independently

of AEs. Only LSRs that require medical intervention (e.g., prescription medication) or require withholding or reduction in dosing frequency of the test articles will be documented as AEs. Any LSRs that are not listed above will be recorded as AEs.

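### The adverse event outcome Recovered/Resolved is met by improvement alone, so an event that is better but still present can be coded as resolved

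*Combined protocol and SAP*

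**What the plan says.** Section 14.1 gives the investigator six outcome categories: Fatal, Not Recovered/Not Resolved, Recovered/Resolved, Recovered/Resolved with Sequelae, Recovering/Resolving and Unknown. Four of them bear on this point:

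- Recovered/Resolved: "AE has improved or the subject has recuperated".
- Recovering/Resolving: "AE is improving or the subject is recuperating".
- Not Recovered/Not Resolved: "AE has not improved or the subject has not recuperated".
- Recovered/Resolved with Sequelae: "subject recuperated but retained the pathological conditions resulting from the prior disease or injury".

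The word resolution also appears in the follow-up rules. Section 14.1 says "AEs should be followed to resolution or stabilization (if possible", and Section 13.2 says that after withdrawal for a related AE, when possible, "the subject should be followed until resolution or stabilization of the AE". Section 14 adds that subjects with AEs "that are present at the end of their participation in the study should receive follow-up as appropriate". None of these rules refers to the outcome code.

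Section 17.3.1 names outcome as an item of the AE listing. The summaries of treatment-emergent AEs in the same section do not use it.

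**The concern.** An outcome field is useful only if the investigator can place each event in one category, and if the category named resolved means that the event is over. As written, an investigator who applies the text exactly may record a persisting reaction as resolved. Another, with an identical case, may record it as resolving or as not resolved.

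This matters somewhat more here than in a large trial. Safety and tolerability is the primary objective (Section 3), Section 14.1 states that the ointment has not been studied in humans, and about 18 subjects at about three sites will be enrolled. With so few subjects, safety is read largely case by case from the listings, so coding differences between sites will not average out. Reactions that are better but still present are also foreseeable. Under Section 10.4, listed local skin reactions that "require withholding or reduction in dosing frequency of the test articles will be documented as AEs", and Section 6.2 lets dosing restart once a reaction has eased substantially, without requiring that it be gone.

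**Working it through.** No figure is at issue, so the check is logical: are the categories mutually exclusive, and where is the field used?

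**Step 1. Test the definitions.** Each of the three definitions has two limbs joined by *or*, so meeting one limb is enough. Take four states of a non-fatal AE and read the text literally:

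| State of the AE | Recovered/Resolved | Recovering/Resolving | Not Recovered/Not Resolved |
|---|---|---|---|
| A. Gone, subject recuperated | met | not met | not met |
| B. Better, still present, still improving, subject not recuperated | met (has improved) | met (is improving) | met (subject not recuperated) |
| C. Better, still present, plateaued, subject not recuperated | met (has improved) | AE limb no longer met | met (subject not recuperated) |
| D. Unchanged or worse | not met | not met | met |

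A and D have one code each. B fits three of the six categories. C fits at least two, with opposite meanings.

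**Step 2. Ask whether other text removes the overlap.** The sequelae category requires recuperation, so there improvement alone does not count; the plain Recovered/Resolved category sets a lower bar. Reading *improved* as *gone* is not supported either: the causality definitions in Section 14.1 speak of improvement when dosing is stopped or reduced, which naturally includes partial improvement. No other section defines resolution.

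**Step 3. Trace the use of the field.**

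- AE listing (Section 17.3.1): onset, severity, therapy required, change in dosing, relationship and outcome. Outcome is one of six items.
- Summaries of treatment-emergent AEs (Section 17.3.1): number of subjects, system organ class, preferred term, severity and relationship. Outcome is not used.
- AE safety endpoint (Section 17.2.1): incidence, with severity and causality. Outcome is not used.

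**Step 4. Repeat the test with the proposed definitions.** A becomes Recovered/Resolved, B becomes Recovering/Resolving, and C and D become Not Recovered/Not Resolved. Each state has one code.

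**The case against.** The strongest reply is that the category names and the change of tense already signal the intended split: Recovered against Recovering, *has improved* against *is improving*. Most investigators would probably place an improving event under Recovering/Resolving. That shows the intent, but the text does not exclude the same event from Recovered/Resolved. For a plateaued event the tense points the wrong way: it has improved and is no longer improving. The CRF completion guidance is not among the documents and may already clarify the terms; that cannot be judged here.

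A reader might also infer larger consequences, which the documents do not support:

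- *Follow-up would end early.* This is only a possibility. Sections 13.2 and 14.1 let follow-up end at stabilization as well as at resolution, no rule is keyed to the outcome code, and Section 14 provides follow-up as appropriate for AEs present at the end of participation.
- *AE duration would be understated.* Duration is not a planned output; Section 17.3.1 names neither duration nor end date.
- *The reversibility of irritation would be overstated in the main tolerability result.* Burning/stinging, pain and pruritus are scored in each Treatment Area at every clinic visit after Screening, independently of AEs (Section 10.4), including Visit 9 (Section 9.7), and are summarized by visit. Erythema, scaling and fissuring are graded at the same visits (Section 10.2). Such a reaction still present at Visit 9 appears in those data whatever its AE code.
- *Many AEs at Visit 9 would be affected.* The documents give no expected count, and Section 10.4 admits the listed local reactions as AEs only when they need medical intervention or a dosing change.

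These replies stand, and they limit the point to the recorded and listed outcome. They do not make the definitions distinct.

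**Conclusion.** The definition is wrong as written: an AE that has improved but persists validly meets the category for resolved events, and no other text corrects this. The consequence is small. One recorded field and one item of the AE listing may overstate recovery or be coded inconsistently across sites. The exposure is clearest for events that the separate skin scales do not capture, such as pigment change or systemic events. No planned endpoint or summary table changes, and no hypothesis test is planned. The conclusion assumes that investigators work from the protocol text and that no unseen CRF guidance overrides it. Severity: minor.

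**What to change.** Replace the three definitions in Section 14.1 and put the same wording in the AE CRF guidance:

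- **Recovered/Resolved:** the AE is no longer present, or the subject is back to the pre-AE state.
- **Recovering/Resolving:** the AE is still present and improving.
- **Not Recovered/Not Resolved:** the AE is still present and not improving, including an AE that improved and then plateaued.

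The sequelae category can stay; the guidance should say that it takes precedence when an event has ended but left a lasting condition. The change costs three lines of protocol and CRF text and alters no visit, endpoint, dose or follow-up rule. Its one downside is that slightly more AEs will be listed as ongoing.

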#### 14.2 Serious Adverse Event

An event that is serious must be recorded on the AE CRF and on the TI SAE Report Form, and requires expeditious handling to comply with regulatory requirements.

An AE or suspected adverse reaction is considered “serious” if, in the opinion of either the investigator or Sponsor, it results in any of the following outcomes:

- Death.
- Life-threatening event.
- Inpatient hospitalization or prolongation of existing hospitalization.
- Persistent or significant incapacity or substantial disruption of the ability to conduct normal life functions.
- Congenital anomaly/birth defect.
- Is an important medical event – defined as a medical event(s) that may not result in death, be life-threatening, or require hospitalization but, based upon appropriate medical judgment, may jeopardize the patient/subject and may require medical or surgical intervention to prevent one of the outcomes listed in the definition above. Examples of such medical events include allergic bronchospasm requiring intensive treatment in an emergency room or at home, blood dyscrasias or convulsions that do not result in inpatient hospitalization, or the development of drug dependency or drug abuse.
- **Although not defined as an AE, pregnancy shall be considered as a serious event and must be immediately reported by telephone to the Medical Monitor and, in the event that he/she is unavailable, to the Project Manager listed on**

**the first page of the protocol.**

Events NOT considered to be serious AEs are:

- Hospitalizations for the treatment, which was elective or pre-planned, of a pre-existing condition that did not worsen, and
- Treatment on an emergency, outpatient basis, for an event not fulfilling any of the definitions of “serious” given above and not resulting in hospital admission.

AEs classified as “serious” by either the investigator or the Sponsor require expeditious handling and reporting to TI to comply with regulatory requirements. **All SAEs, whether related or unrelated to test article, must be immediately reported by telephone to the Medical Monitor [contact]) and, in the event that he/she is unavailable, to the Project Manager [contact], [name]) [additional contact information listed on the first page of the protocol].** Written notification of all SAEs should be sent to the Project Manager by email or confirmed facsimile transmission. These include those SAEs listed in the protocol or IB and must include an assessment of whether there is a reasonable possibility that the drug caused the event.

Study endpoints that are SAEs (e.g., all-cause mortality) must be reported in accordance with the protocol unless there is evidence suggesting a causal relationship between the drug and the event (e.g., death from anaphylaxis). In this case, the investigator must immediately report the event to the Sponsor. In addition, such information should also be provided to the site’s respective IRB per their governing guidelines for SAE reporting.

If only limited information is initially available, follow-up reports are required. Should the investigator become aware of a SAE (regardless of its relationship to test article) that occurs within 30 days after stopping the test article, the SAE must be reported in accordance with procedures specified in this protocol. In the event of death, if an autopsy is performed, a copy of the report should be sent to TI, if available.

As required, TI will notify participating investigators of all suspected adverse reactions that are serious and unexpected. This notification will be in the form of an IND safety report of potential serious risks as soon as possible but no later than 15 calendar days after the Sponsor determines that the information is “reportable” according to the criteria listed in 21 CFR Section 312.32. These are:

- i) Serious and unexpected suspected adverse reactions,
- ii) Findings from other studies including epidemiological studies, pooled analyses or other clinical studies that suggest a significant risk in humans exposed to the test articles,
- iii) Findings from animal or in vitro tests that suggest a significant risk to humans exposed to the test articles, or reports of significant organ toxicity at or near the expected human exposure, and
- iv) Clinically important increases in the rate of occurrence of serious suspected

- adverse reactions.
- v) Confirmed pregnancy at any time during the study or within one month from discontinuing from the study.

Upon receiving such notices, the investigator must review and retain the notice with the IB and immediately submit a copy of this information to the responsible IRB according to local regulations. The investigator and IRB will determine if the informed consent/assent requires revision. The investigator should also comply with the IRB procedures for reporting any other safety information. Where required, submission of safety updates by the investigator to Health Authorities should be handled according to local regulations.

